#### **6.0 STATISTICAL CONSIDERATIONS**

This Post Marketing Clinical Follow-up (PMCF) study is designed to confirm the performance of the DESyne X2 Novolimus Eluting Coronary Stent System with regards to the residual risks of lesion access and acute device implantation through visually-assessed angiographic endpoints and physician feedback and demonstrate that these characteristics are not different than the DESyne Novolimus Eluting CSS. The overall result of this study will be summarized descriptively, and examined relative to the clinical results observed in the EXCELLA II Randomized Study.

Data for all categorical endpoints will be summarized with patient counts, percentages, and exact 95% Clopper-Pearson confidence intervals.

One study population will be examined during the analyses: the modified intent-to-treat population (MITT), which will consist of all patients treated with at least one DESyne X2 stent.

While this post marketing study is not powered to determine extremely rare events, a sample size of 100 patients is sufficient to detect rare, acute device related performance issues.

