### 3.5.7 Other Follow-up Guidelines

There may be situations where an attempt to treat the patient with the DESyne X2 stent is made, but the procedure is stopped prior to the stent being delivered to the target site (i.e., the stent is introduced into the guiding catheter and circulation but patient becomes unstable, power outage, etc.). In these situations, the patient will be deregistered from the study and treated per standard hospital practice.

In the situation where an attempt to treat the patient with the DESyne X2 stent is made but due to a device malfunction or failure to cross the lesion, no DESyne X2 stent is subsequently implanted, the case shall be noted as not meeting the Device Success endpoint. All device failures will be recorded and reported.

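### The only analysis population in Section 6.0 leaves out delivery failures that Section 3.5.7 counts against Device Success, so the success rate is biased upward

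*Combined protocol and SAP*

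**What the plan says.** **Who is analysed.** Section 6.0 provides for a single population, the MITT, "which will consist of all patients treated with at least one DESyne X2 stent".

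**What counts as a failure.** Section 3.5.7 deals with an attempted X2 treatment that is defeated by a malfunction or by failure to cross. If "no DESyne X2 stent is subsequently implanted, the case shall be noted as not meeting the Device Success endpoint". It adds: "All device failures will be recorded and reported". Section 3.5.4 has failure to implant at the intended site entered on the case report form as a treatment failure.

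**Who is enrolled.** Section 5.0 counts a patient as enrolled once the device has entered the body, subject only to withdrawal by the patient or the physician. Section 3.5.7 also says that if a procedure is stopped before the stent reaches the target, for reasons such as instability or a power outage, "the patient will be deregistered from the study and treated per standard hospital practice".

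**What the study claims.** Sections 1.0, 2.3 and 6.0 state an aim to "demonstrate that these characteristics are not different than the DESyne Novolimus Eluting CSS". Section 1.0 also says the study will confirm similar delivery-system performance. Section 6.0 then states: "The overall result of this study will be summarized descriptively, and examined relative to the clinical results observed in the EXCELLA II Randomized Study". The method is: "Data for all categorical endpoints will be summarized with patient counts, percentages, and exact 95% Clopper-Pearson confidence intervals".

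**The concern.** Section 2.2 says the delivery system is the main difference between X2 and its predecessors. Section 2.3 says the study is about lesion access and acute implantation, and links both to the updated delivery system. A device that malfunctions or will not cross, and leaves the patient without an X2 stent, is the most direct evidence on that question. Section 3.5.7 scores such a case as a failure, but under Section 6.0 the patient is in neither the numerator nor the denominator of the Device Success rate. Both instructions cannot be followed for the same rate.

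If the report follows Section 6.0, the headline success rate and its exact interval describe only patients in whom at least one delivery worked. That rate would then be set beside historic DESyne results and read as support for similar performance.

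**Working it through.** **1. Is the failed patient enrolled?** Yes. The device was introduced, so Section 5.0 applies. The deregistration rule in Section 3.5.7 covers procedures stopped for other reasons; its next paragraph handles malfunction and failure to cross separately.

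**2. Is the failed patient in the MITT?** On the natural reading, no. Section 6.0 requires treatment with at least one X2 stent. Section 3.5.7 separates an attempt to treat from implantation, and Section 3.5.4 describes non-implantation as being unable to treat with the study stent.

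**3. Direction of the bias.** Let N be the enrolled patients with attempted delivery (no deregistered cases), f those with no X2 stent because of malfunction or failure to cross, and g the other Device Success failures.

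- Counted as in Section 3.5.7: (N − f − g)/N
- Counted in the MITT: (N − f − g)/(N − f)

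The MITT rate is the first rate multiplied by N/(N − f). That factor exceeds 1 whenever f is at least 1, so the shift can only be upward.

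**4. Size.** N = 100 is the planned maximum. The documents give no failure or success rates, so f and g are assumptions. The intervals are the exact 95% Clopper-Pearson intervals that Section 6.0 specifies. When x = n, the lower limit is 0.025^(1/n); for example, 0.025^(1/97) = 0.963.

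| f | g | MITT | 95% CI | Counted per 3.5.7 | 95% CI |
|---|---|---|---|---|---|
| 1 | 0 | 99/99 = 100% | 96.3 to 100 | 99/100 = 99% | 94.6 to 100.0 |
| 3 | 0 | 97/97 = 100% | 96.3 to 100 | 97/100 = 97% | 91.5 to 99.4 |
| 5 | 0 | 95/95 = 100% | 96.2 to 100 | 95/100 = 95% | 88.7 to 98.4 |
| 2 | 1 | 97/98 = 99.0% | 94.5 to 100.0 | 97/100 = 97% | 91.5 to 99.4 |

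With five such failures, the rate counted per Section 3.5.7 (95%) lies below the whole MITT interval (96.2 to 100).

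**5. The plan's own figure.** Section 6.0 says that "a sample size of 100 patients is sufficient to detect rare, acute device related performance issues". No rate or power is given, so 100 cannot be re-derived. As a plausibility check, the chance of at least one event in 100 patients is 1 − (1 − p)^100: 63.4% at p = 1%, 86.7% at 2% and 95.2% at 3%. The statement is therefore reasonable for issues at about 3%, provided the patients who have the issue are counted.

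**6. The wording point.** The plan has no margin, performance goal, difference interval or decision rule, and states no historic DESyne acute success rate. The EXCELLA II results quoted in Section 2.1 are late lumen loss, volume obstruction and a clinical composite. To show how little near-equal rates settle, assume 98/100 for X2 and three possible DESyne results. The Newcombe 95% intervals for X2 minus DESyne, in percentage points, are:

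- against 69/70: −5.7 to +5.8
- against 103/105: −5.3 to +4.9
- against 137/140: −5.1 to +4.4

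The counts and arm sizes are assumptions. The intervals leave room for a difference of about 4 to 6 points in either direction.

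**The case against.** **The failures are not hidden.** Section 3.5.7 is the specific rule for these cases, and it requires them to be noted as endpoint failures, recorded and reported. That stands, and a reader who infers that the plan conceals delivery failures goes too far. But a listing does not put the patients into the rate or its interval.

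**The MITT wording is open.** Section 6.0 does not define what it means to be treated with a stent, and an attempted treatment might be meant. Sections 3.5.4 and 3.5.7 point the other way, but the ambiguity is real. A reader might infer that a delivery failure can never appear in the success rate. That holds only if Section 6.0 overrides Section 3.5.7 and the patient received no X2 stent in any lesion. A patient with one failed delivery who still receives an X2 stent stays in the MITT.

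**A descriptive study is acceptable here.** Agreed. Immediately after stating the aim, Section 6.0 says the results will be summarised descriptively, and it plans no test. A reader might infer that a formal equivalence claim is planned, or that 100 patients is the wrong number. The documents support neither, so the wording issue is minor.

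**A new denominator has its own gaps.** Sections 5.0 and 3.5.7 disagree about patients whose procedure stops after introduction: one enrols them, the other deregisters them. Physician withdrawal is a further way out of the denominator. A malfunction during preparation comes before introduction, so a denominator based on introduction would miss it too; it would have to be reported under the physician feedback and malfunction items. These points shape the fix but do not remove the conflict.

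**Conclusion.** The main point holds. On its natural reading, the sole population in Section 6.0 conflicts with Sections 3.5.7 and 5.0, and following Section 6.0 biases Acute Device Success upward for the component the study is meant to check. The bias has a certain direction once any such failure occurs, but an unknown size. Three to five failures per 100 would turn 97% or 95% into a reported 100%. Those counts are illustrative and assume no deregistered patients, no other failures, and no X2 stent in another lesion of a failed patient.

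The secondary point, that the stated aim claims more than a descriptive analysis can show, is real but minor. The population should be corrected before analysis; the wording can be corrected in the same amendment.

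**What to change.** **Population (Section 6.0).**

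- Make the primary population for Acute Device Success all enrolled patients in whom X2 delivery was attempted (device introduced, as in Section 5.0), except procedures stopped before delivery for the non-device reasons that Section 3.5.7 deregisters.
- Count a malfunction or failure to cross with no X2 stent implanted as a failure.
- Reconcile enrolment on introduction (Section 5.0) with deregistration (Section 3.5.7), and report the number of deregistered and withdrawn patients with the reason for each.
- Keep the MITT as a secondary summary and say that it means patients with at least one X2 stent implanted.

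**Wording (Sections 1.0, 2.3 and 6.0).** Drop the promise to demonstrate no difference, and in Section 1.0 the statement that the study will confirm similar performance. Keep the historic comparison in descriptive form, for example: *describe X2 acute device success with its exact 95% CI and present historic DESyne acute performance data alongside as context*. Give the source, x/n and success definition of the historic figure.

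**Cost.** Text edits and no extra patients. Section 3.5.4 already puts failure to implant on the case report form. No section says that data are kept on deregistered patients, so a count and reason would have to be logged for them. The reported success rate may be lower and the stated claim more modest.

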## 1.0 DESyne X2 PMCF PROTOCOL SUMMARY

Design:	Prospective, non-randomized, multicenter, international Post Marketing Clinical Follow-up (PMCF) study				
Enrollment:	Enrollment of up to 100 patients with up to three de novo native coronary artery lesions measuring between 2.25 and 4.0 mm in diameter and $\leq 34$ mm in length receiving the DESyne X2 Novolimus Eluting Coronary Stent System (CSS).				
Clinical Site Locations:	Drawn from up to 10 International Sites				
Objective and Rationale:	
To confirm the performance of the DESyne X2 Novolimus Eluting Coronary Stent System with regards to the residual risks of lesion access and acute device implantation through visually-assessed angiographic endpoints and physician feedback and demonstrate that these characteristics are not different than the DESyne Novolimus Eluting CSS.
 
A single-arm study comparing the DESyne X2 PMCF data to the historic DESyne acute performance data will confirm that the DESyne X2 delivery system performs similarly to the DESyne delivery system.
				
Key Endpoints:	
Acute Device Success: attainment of final result with <math>< 50\%</math> residual stenosis of the target site, using a DESyne X2 stent and standard predilatation catheters and post-dilatation catheters (if applicable)
 
Device preparation
 
Lesion access and cross
 
Stent expansion
 
Delivery system removal
 
Stent crossability for post-dilatation as required
 
Device malfunction assessment
				
Time Course:	
 
 Initial Enrollment	Q3 2020	
 
 Enrollment Complete	Q2 2021	
 
	Initial Enrollment	Q3 2020	Enrollment Complete	Q2 2021
Initial Enrollment	Q3 2020				
Enrollment Complete	Q2 2021				
Inclusion Criteria:	
Candidates for this study must meet all of the following criteria:
 
 
1) The patient must be <math>\geq 18</math> years of age.
 
2) The patient must have stable angina pectoris as defined by the Canadian Cardiovascular Society Classification, documented silent ischemia, acute coronary syndrome, or a positive functional study requiring treatment
 
3) The patient is considered a candidate for coronary stent implantation and has a planned intervention of up to
 
				

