**“DESyne X2 PMCF Study”**

**ELX-CL-1705**

**Revision C**

**Date: 18 September 2020**

## **2.0 INTRODUCTION**

### **2.1 Background and Rationale**

Pertinent prior clinical experience with Elixir’s DESyne or DESyne BD Novolimus Eluting Coronary Stent System (CSS) includes two randomized studies: the EXCELLA II Randomized Study - Phase 1 and the EXCELLA II Randomized Study – Phase 2.

The EXCELLA II Randomized Clinical Trial - Phase 1 was a single blind, consecutive enrollment, non-inferiority trial which enrolled a total of 210 patients at 21 international sites wherein the Principal Investigator was [name], MD, PhD. Co-Principal Investigators included [name], PhD, [name] and [name]. The study was designed to evaluate the safety and efficacy of the Elixir DESyne Novolimus Eluting Coronary Stent System as compared to the Endeavor Zotarolimus Eluting Coronary Stent System (Medtronic Vascular, Santa Rosa, CA). The primary endpoint for this study was the in-stent late lumen loss assessed by QCA at 9 months. Key secondary endpoints included the device-oriented composite endpoint (DoCE) inclusive of cardiac death, myocardial infarction attributable to the target lesion and clinically-indicated target lesion revascularization evaluated at 30 days, 6, 9, 12 and 24 months. The in-stent percent volume obstruction (%VO) was measured in a sub-group of 65 patients having 9-month intra-vascular ultrasound (IVUS) follow-up.

At 9-months, the in-stent late lumen loss was  $0.11 \pm 0.32$  mm in the DESyne stent arm, as compared to  $0.63 \pm 0.42$  mm in the Endeavor stent arm ( $p < 0.001$  non-inferiority,  $p < 0.001$  superiority). In-stent %VO by IVUS was  $4.5 \pm 5.1\%$  and  $20.9 \pm 11.3\%$  for the DESyne stent and the Endeavor stent, respectively ( $p < 0.001$ ). There was a significant difference between stent groups in the device orientated composite endpoint (DESyne 7.9% vs.

Endeavor 19.7%,  $p=0.02$ ) indicating superior clinical results driven primarily by the reduction in TLR for the DESyne stent.

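### Section 6.0 plans an interval for X2 alone and none for the X2-versus-DESyne comparison the study is meant to make

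*Combined protocol and SAP*

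**What the plan says.** The Protocol Summary (Section 1.0, Objective and Rationale) describes "A single-arm study comparing the DESyne X2 PMCF data to the historic DESyne acute performance data", and Section 2.4 repeats the comparison. Section 6.0 gives the aim as to "demonstrate that these characteristics are not different than the DESyne Novolimus Eluting CSS".

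For the analysis, Section 6.0 says: "The overall result of this study will be summarized descriptively, and examined relative to the clinical results observed in the EXCELLA II Randomized Study". Its only inferential tool is this: "Data for all categorical endpoints will be summarized with patient counts, percentages, and exact 95% Clopper-Pearson confidence intervals". It names one population, "which will consist of all patients treated with at least one DESyne X2 stent", so every planned interval describes X2 and nothing else.

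The section plans no interval for a difference, no test and no margin, and it gives no DESyne rate with a denominator. It does not say which phase of EXCELLA II is meant. Section 2.1 shows that Phase 1 is the one that used DESyne, and that it "enrolled a total of 210 patients at 21 international sites" across both arms. The size of the DESyne arm is not given.

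**The concern.** The question concerns two devices, and the error bars concern one. The historic DESyne rate was also estimated from a finite sample, so the difference between the two rates is less certain than the X2 rate alone.

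If the final report sets the X2 interval beside a DESyne percentage, two misreadings become possible. A DESyne rate just outside the interval would look like a real difference when the two samples together do not support one. A DESyne rate inside it would suggest a narrower range of compatible differences than the data allow. The second matters more here, because the aim is to say that the devices do not differ.

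**Working it through.** **Inputs.** X2 sample size: 100, the enrolment ceiling and the figure in Section 6.0, assuming all 100 are analysed with one outcome each. The historic acute success rate and its denominator are not in the documents. True success is therefore an assumption, tried from 90% to 99% and taken as equal for both devices.

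**The plan's own figure.** Section 6.0 calls 100 patients enough to detect rare device problems, but gives no event rate, power or margin, so there is no calculation to reproduce.

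**Inferring the DESyne arm.** Section 2.1 reports a device-oriented composite of 7.9% against 19.7% (p=0.02) in 210 patients. If all 210 are counted, only two splits give both percentages after rounding:
- DESyne 11/139 and Endeavor 14/71, Fisher p=0.022
- DESyne 5/63 and Endeavor 29/147, Fisher p=0.040

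The first fits the reported p-value better, so 139 is the working value and 63 the alternative. The whole trial, 210, bounds what one arm of it could hold.

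**Standard error of the comparison.** With equal true rates, the ratio of the standard error of the difference to that of X2 alone is √(1 + 100/n₀), where n₀ is the DESyne sample size:
- n₀=139: √1.719 = 1.31
- n₀=63: √2.587 = 1.61
- n₀=210: √1.476 = 1.21

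**If the X2 interval were read against a DESyne percentage.** Take X₁ ~ Bin(100, p) and X₀ ~ Bin(n₀, p), and sum exactly the probability that X₀/n₀ lies outside the 95% Clopper-Pearson interval for X₁/100:

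| True success | n₀=63 | n₀=139 | n₀=210 |
|---|---|---|---|
| 90% | 20.4% | 10.6% | 8.3% |
| 95% | 20.5% | 10.2% | 8.0% |
| 97% | 23.9% | 10.0% | 7.4% |
| 98% | 29.2% | 10.3% | 7.3% |
| 99% | 34.9% | 16.5% | 10.3% |

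At n₀=139, a 95% Newcombe interval for the difference excludes 0 in 4.3%, 4.2%, 2.7%, 1.6% and 0.5% of studies, down the same rows.

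**Example with the DESyne rate outside.** X2 95/100 has a Clopper-Pearson interval of 88.7% to 98.4%, which excludes DESyne 137/139 = 98.6%. For Newcombe, the Wilson limits are 88.8% to 97.8% for X2 and 94.9% to 99.6% for DESyne. The difference is 95.0 − 98.6 = −3.6 points, with limits
- lower: −3.56 − √(6.17² + 1.04²) = −9.8
- upper: −3.56 + √(2.85² + 3.66²) = +1.1

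This interval includes 0.

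**Example with the DESyne rate inside.** X2 97/100 has an interval of 91.5% to 99.4%. DESyne 136/139 = 97.8% lies inside it. Subtracting 97.8 from the X2 limits suggests differences from −6.4 to +1.5 points. Newcombe gives −6.5 to +3.6, so the one-sample reading understates the range, here almost entirely on the upper side.

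**The case against.** The strongest reply is that the plan never commits to the reading tested above. Section 6.0 calls the summary descriptive and says results will be "examined relative to the clinical results observed in the EXCELLA II Randomized Study". It has no rule that checks whether the X2 interval covers a DESyne percentage, and it does not rule out showing DESyne with its own interval. Clopper-Pearson is a sound choice for describing X2. This stands. A reader might infer that the plan contains a test whose false-difference rate is about double the nominal 5%. The documents do not support that, because no such test is written.

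The inputs are also uncertain. The 139 is inferred from a clinical composite, not from an acute endpoint, and assumes all 210 patients were counted. The Protocol Summary refers only to historic DESyne acute data, which need not be one arm of one trial. With an illustrative 300 historic patients the figure falls to about 4-7%, close to nominal. This stands too, and it is why the sizes are conditional.

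Finally, a false difference is not the error that most threatens the stated aim. At n₀=139 and 98% true success, 9.2 of the 10.3 percentage points come from X2 looking worse than DESyne, which counts against the sponsor's own device. This also stands: the lasting problem is the missing uncertainty for the difference, and the false-difference rate only illustrates it.

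The descriptive label does not remove the gap. A descriptive comparison still needs to describe the difference and its precision, and the same section speaks of demonstrating a result.

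**Conclusion.** The concern holds in a limited form. Section 6.0 states a comparative aim and plans no uncertainty for the comparison. Its only interval leaves out the sampling error of the historic rate. That follows from the text and needs no assumption about arm size.

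The size is conditional on full enrolment of 100, equal true rates, and a reader setting the X2 interval against a DESyne percentage. On that footing the DESyne rate falls outside in about 10% of studies for an arm of 139 and true success of 90-98%, and in about 17% at 99%. It is 20-35% for the less well-fitting arm of 63, and 7-10% for 210. A general claim that the error doubles would go too far, since the documents give neither the historic rate nor its denominator and the multiple changes with both.

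A two-sample interval would also not settle the stated aim. With no margin, an interval that includes 0 is not in itself evidence that the devices perform alike.

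**What to change.** In Section 6.0:
- State the historic DESyne numerator and denominator, and their source, for each endpoint recorded for both devices.
- Report the X2-minus-DESyne difference in proportions for each of these, with a two-sided 95% Newcombe or Miettinen-Nurminen interval.
- Rest statements about X2 relative to DESyne on that interval, and keep Clopper-Pearson for describing X2 alone.
- Say that an interval including 0 does not by itself show absence of a difference, and that the conclusion will report the range of differences the interval leaves open.

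The cost is a few sentences and one more calculation per endpoint, with no added patients or visits. It does require the sponsor to retrieve the acute counts from its own DESyne trial. The downside is that the comparison looks less favourable: its standard error is about 30% larger than that of X2 alone at n₀=139, and in the 97/100 example the interval widens from 7.9 to 10.1 points.

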**Confidential and Proprietary**

Nothing herein is to be disclosed, reproduced or copied  
without the express written consent of Elixir Medical

PROTOCOL AMENDMENT SUMMARY OF CHANGES

*In this amendment the Sponsor is adding into the study the following: the 2.25mm stent in 14, 18, 23, 28, 32, and 38mm lengths, and an update to the inclusion and exclusion criteria to allow enrollment of a broader range of patients. A few minor administrative updates are also included. A Table of Changes for the protocol is provided below. These changes neither affect subjects’ rights, safety and welfare, nor the scientific soundness of the study. The Coordinating Investigators and Principal Investigators have been updated on the changes.*

Protocol	Change to protocol	Location in Protocol / Section Number	Rationale
ELX-CL-1705 Rev B	ELX-CL-1705 Rev C		
Stent sizing included 2.5 mm – 4.0mm diameters in the 14, 18, 23, 28, 32, and 38 mm lengths	Stent sizing included 2.25 mm – 4.0mm diameters in the 14, 18, 23, 28, 32, and 38 mm lengths	Protocol Summary, Sections 2.2 and 3.5.2	The inclusion of 2.25mm stent in 14, 18, 23, 28, 32 and 38mm lengths will allow enrollment of a broader range of patients
Inclusion/Exclusion Criteria	Changes to inclusion/exclusion criteria	Protocol Summary, Sections 3.1, 3.2, 3.3 and 3.5.2	
Inclusion are broadened and exclusion criteria reworded to allow a wider range of patient inclusion. These changes include:
 
 
• Single site inclusion of up to 40 patients or (40% of the total patients)
 
• No 4. Inclusion of 2.25mm lesions, and inclusion of up to 3 lesions in separate epicardial vessels.
 
• Exclusion criteria: No. 3. clarification of previous stent implantation location (removal of “distal”);
 
• replacement of No. 8 “Lesion involvement of a significant side branch (branch diameter > 2 mm) that would be covered by stenting” with “Bifurcation lesion with planned 2-stent technique”;
 
• rewording of No. 11 MI exclusion to “Patient has a diagnosis of ST elevation myocardial infarction (STEMI) within 72 hours preceding the index procedure, and CK and CK-MB have not returned within normal limits at the time of procedure”;
 

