## **2.2 DESyne® X2 Novolimus Eluting Stents Coronary Stent System**

The DESyne® X2 Novolimus Eluting Coronary Stent Systems is comprised of four key components including the delivery system, stent, the active drug substance Novolimus, and polymer that controls the release of the drug. The stent, drug substance, drug dose, and polymer of the DESyne X2 NECSS are the same as those used in the DESyne NECSS. The stent, drug substance, and drug dose are the same as those used in the DESyne BD NECSS. The main difference between the DESyne X2 NECSS and the DESyne and DESyne BD NECSS is the delivery system used on the DESyne X2 NECSS. The updated delivery system is used in the same manner and has the same accessory compatibility as the DESyne and DESyne BD delivery systems. The delivery systems have differences with respect to dimensions and materials; however these dimensions and materials similar to other percutaneous balloon delivery systems.

---

The DESyne X2 delivery system provides a means for carrying the stent through the coronary vasculature to the desired location and expanding the stent through inflation of the balloon. The delivery system is comprised of standard materials with a stainless steel hypotube proximally, a nylon blend shaft distally and nylon blend balloon. The premounted stent is made of cobalt chromium alloy. It is available in diameters of 2.5 mm, 2.75 mm, 3.0 mm, 3.5 mm and 4.0 mm with lengths of 14 mm, 18 mm, 28 mm, 32 mm and 38 mm^2. The stent has a nominal strut thickness of 0.0032" (0.08 mm) with an 8-crown pattern for the 3.0, 3.5, and 4.0 mm sizes and a 6-crown pattern for the 2.25, 2.5 and 2.75 mm sizes. The DESyne X2 delivery system is substantially similar to the DESyne and DESyne BD delivery systems.

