### 2.3 Risk Assessment

The Elixir DESyne and DESyne BD Novolimus Eluting Coronary Stent Systems have demonstrated excellent clinical safety and efficacy in both the EXCELLA II Randomized Study – Phases 1 and 2. Both of these systems have received CE Mark approval. A post market clinical follow-up study of the DESyne X2 device, which has also received CE Mark approval, is desired to confirm the performance of the DESyne X2 Novolimus Eluting Coronary Stent System with regards to the residual risks of lesion access and acute device implantation through visually-assessed angiographic endpoints and physician feedback and demonstrate that these characteristics are not different than the DESyne Novolimus Eluting CSS. These attributes are most directly related to the performance of the updated delivery system, including stent mounting on the delivery system balloon.

The safety profile and the known mechanism of action of the drug, Novolimus, and the biocompatibility of both the durable methacrylate polymer coating in combination with the scaffolding properties of the DESyne CSS provide a safe and effective method for reducing neointimal hyperplasia. Therefore, the benefits of the acute lesion scaffolding and long-term reduced incidence of restenosis in the treatment of ischemic coronary artery disease have already been demonstrated to outweigh the risks associated with the use of these devices and are applicable to the DESyne X2 NECSS. The use of the DESyne X2 NECSS has the same risk profile as the DESyne NECSS and the DESyne BD NECSS. No differences in risk or the risk/benefit ratio are expected with the use of the updated delivery system of the DESyne X2 NECSS.

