### 4.1 Lesion, vessel, and stent characteristics

Lesion, vessel, and stent characteristics recorded in the source documentation should include:

- Estimated reference vessel diameter (target lesion)
- Estimated lesion length
- Estimated % DS (target lesion)

- Number of stents used
- Stent brand
- Vessel (LAD, LCX, RCA, Left Main)
- Lesion location (ostial, proximal, mid, distal, branch)
- Stent diameter (mm)
- Stent length (mm)
- Lot number of the DESyne X2 stent
- Success of stent implantation or device malfunction details

**Note:** Maintain a copy of all of the index procedure angiography for possible analysis by an angiographic core laboratory.

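### Section 6.0 plans one pooled patient-level result with no summary by stent size or number of lesions, so a delivery problem confined to the new 2.25 mm size may be diluted

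*Combined protocol and SAP*

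**What the plan says.** Section 6.0 defines a single analysis set: "One study population will be examined during the analyses". That set is the MITT group, meaning everyone who received one or more X2 stents. On method it says: "Data for all categorical endpoints will be summarized with patient counts, percentages, and exact 95% Clopper-Pearson confidence intervals". The overall result is to be described and looked at against EXCELLA II, with the aim of showing that acute performance does not differ from DESyne. No summary by stent diameter, stent length or number of lesions is planned, and no matching or adjustment.

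The Revision C amendment summary gives this reason for the new size: "The inclusion of 2.25mm stent in 14, 18, 23, 28, 32 and 38mm lengths will allow enrollment of a broader range of patients". Current Section 3.2 admits reference diameters from 2.25 mm and up to three lesions. Section 3.3 excludes bifurcations only where two stents are planned. Apart from administrative corrections throughout, the amendment summary lists no change to Section 6.0.

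Section 2.3 says of the characteristics under study: "These attributes are most directly related to the performance of the updated delivery system, including stent mounting on the delivery system balloon". Section 2.2 describes two strut designs, with "a 6-crown pattern for the 2.25, 2.5 and 2.75 mm sizes" and an 8-crown pattern for 3.0 to 4.0 mm. Section 4.1 already has stent diameter, stent length, vessel and lesion measurements, and malfunction details recorded for each case. Section 3.5.7 requires every device failure to be documented and reported.

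**The concern.** The study asks whether a new delivery system gets the stent to the lesion and expands it as well as the old one did. The system is made in several diameters and lengths, and it is plausible, though not shown in the documents, that access and expansion vary with size and vessel. If so, one pooled percentage can mislead in two ways.

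- **Dilution.** A high failure rate in a small subgroup, such as the newly added 2.25 mm size, can sit inside a reassuring overall figure. A narrow pooled interval may then be read as if it covered that size.
- **Shift without a device effect.** Device Success is defined per target site (Section 4.0), but Section 6.0 counts patients. If more lesions are treated per patient, or more difficult ones, the patient-level rate can fall with an identical device.

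The conclusion of similarity to DESyne rests on this one comparison.

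**Working it through.** **The plan's own figure.** Section 6.0 says that "a sample size of 100 patients is sufficient to detect rare, acute device related performance issues". It gives no event rate, power, margin or reference rate, so 100 cannot be re-derived. What it delivers follows from P(at least one event) = 1 − (1 − p)^100: 63.4% at p = 1%, 86.7% at 2% and 95.2% at 3%. That holds for all sizes together.

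**Inputs not in the documents.** The number of 2.25 mm cases, all failure rates, and the EXCELLA II entry criteria, sizes, lesion counts and acute success rate are not given. The counts and rates below are assumptions.

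**Dilution.** Assume 100 patients with one lesion and one stent each, 10 of them at 2.25 mm.

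| Group | Failures | Rate | Exact 95% interval |
|---|---|---|---|
| 2.25 mm | 2/10 | 20% | 2.5% to 55.6% |
| Other sizes | 1/90 | 1.1% | 0.03% to 6.0% |
| Pooled | 3/100 | 3% (97% success) | success 91.5% to 99.4% |

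A study with 1 failure in 100 would report 99% success (94.6% to 99.97%). The two pooled intervals overlap widely, although one size fails in a fifth of cases.

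In expectation, with 1% failure in other sizes and 10% at 2.25 mm, the pooled failure rate is [n × 10% + (100 − n) × 1%] / 100. This gives 1.45% for n = 5, 1.9% for n = 10, 2.8% for n = 20 and 3.7% for n = 30.

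**What zero failures would mean.** The exact upper limit for 0/n is 1 − 0.025^(1/n).

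| n | Upper limit |
|---|---|
| 100 (pooled) | 3.6% |
| 30 | 11.6% |
| 20 | 16.8% |
| 10 | 30.8% |
| 5 | 52.2% |

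**Lesion count.** Section 6.0 does not say how a patient with several lesions is scored. Assume that any failed lesion fails the patient and that lesions are independent. With a 2% per-lesion failure rate, patient-level failure is 2% for one lesion, 1 − 0.98² = 4.0% for two and 1 − 0.98³ = 5.9% for three.

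**Case difficulty.** Assume 99% success in simple and 95% in complex cases. With 10% complex, the pooled rate is 0.9 × 99% + 0.1 × 95% = 98.6%. With 40% complex it is 0.6 × 99% + 0.4 × 95% = 97.4%. The device is the same in both.

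**Who is counted.** Under Section 3.5.7, a malfunction or failure to cross that ends with no X2 implanted does not meet Device Success. If treated with a stent means that one was implanted, which is the natural reading, such a patient falls outside the Section 6.0 population. Size tables built on that population could lose the very failures they are meant to show.

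**The case against.** The strongest reply is that this is a descriptive, single-arm post-market study of a CE-marked device, deliberately broadened, and that an overall rate in the intended population is a legitimate summary. That stands. So do several limits on how far the point can be taken.

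- A reader might infer that the plan rules out breakdowns. It does not: the sentence on one population defines the analysis set. The gap is only that no breakdown is planned.
- A reader might infer that a 2.25 mm problem would be hidden. That goes too far. Failures must be reported, and size and malfunction details are recorded, so each failure can be traced to its size. A listing of failures still has no size-specific denominator or interval, so dilution in the summary percentage is what remains.
- A reader might infer that the X2 population is wider than that of EXCELLA II. Revision C widened entry relative to Revision B. The documents do not give EXCELLA II's entry criteria, sizes or lesion counts, or say how acute stenosis was read there. Unmatched case mix is a risk of any historical comparison, not a demonstrated difference.
- Subgroups would be small, and tables do not make failures easier to observe. At an assumed 5% rate, the chance of no 2.25 mm failure is 0.95^10 = 60% with 10 cases and 0.95^20 = 36% with 20, whether or not a table is planned. The tables stop an empty cell from being read as reassurance; they cannot rule a problem out.

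**Conclusion.** The point holds as an inexpensive improvement to the analysis plan, not as a flaw that undermines the study. Section 6.0 plans no summary by size or lesion count after both were widened, and the pooled figure could dilute a size-specific problem: 20% failure in 10 cases can coexist with 97% overall success. The pooled upper limit of 3.6% for zero failures does not carry over to the new size, where it would be 16.8% with 20 cases or 30.8% with 10.

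These sizes rest on assumed counts and rates; the planned number of 2.25 mm cases is not stated. The lesion-count effect also rests on an assumed scoring rule and independence. The documents support neither the claim that case mix differs from EXCELLA II nor a matched subset as the main comparison.

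**What to change.** Add to Section 6.0:

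1. Descriptive tables of Device Success, lesion access and cross, and device malfunction by stent diameter (2.25 mm alone, 2.5 to 2.75 mm, 3.0 to 4.0 mm) and by number of treated lesions, with exact intervals. The 2.25 mm size is shown alone because it is new in Revision C; by crown pattern it belongs with 2.5 and 2.75 mm.
2. The unit of analysis: lesion or device for the size tables, with a note that lesions within a patient are not independent and the exact interval is then approximate; patient for the lesion-count tables, with the scoring rule for several lesions stated.
3. A denominator of all attempted X2 cases, so that malfunctions and failures to cross with no X2 implanted are kept.
4. A sentence that the pooled interval does not apply to the 2.25 mm size alone.
5. Lesion and size mix shown beside the EXCELLA II data where these are available. A comparison restricted to comparable X2 cases may be added as supportive only.

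The table categories also need consistent source text. Section 2.5 says up to two lesions, while Sections 3.2 and 3.5.2 say up to three. The diameter list in Section 2.2 omits 2.25 mm and the list in Section 3.5.2 omits 2.5 mm. These passages must be reconciled.

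Size and malfunction details are already recorded under Section 4.1. The cost is a few extra tables with wide intervals, which would describe a size problem but could not exclude one.
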